**Biopsy(ies):**

If there is no confirmation of diagnosis via histology based on a tissue sample obtained within 6 weeks prior to planned infusion, a biopsy will be conducted prior to catheter placement and PVSRIPO infusion to confirm active tumor/high-grade glioma. After the biopsy is performed, the catheter is placed but PVSRIPO may not be infused until the qualifying diagnosis is made.

If the biopsy at catheter placement does not confirm active tumor/high-grade glioma by the site pathologist, the patient will not receive PVSRIPO and will be withdrawn from the study as a screen failure. The catheter should be removed and followed by a CT scan to confirm no bleeding.

Note: for all patients, including patients with tumor transformed from a lower grade to a higher grade, glioblastoma must be confirmed via prior histology by the site pathologist prior to biopsy/catheter placement.

Stereotactic biopsy(ies) and catheter placement will be performed via the site's standard of care prior to PVSRIPO administration, unless specified below.

- After biopsy for confirmation of diagnosis (if required), if there is sufficient tissue available, up to three additional core biopsies will be obtained to undergo planned future molecular genetic testing as described in **Section 5.7.4**. If no additional biopsies are obtained but archival tissue is available within 6 weeks prior to infusion, that tissue will be requested/utilized for future testing.
  - For patients retreated with PVSRIPO, tissue for tumor typing and clinical pathologic testing per SOC should be obtained prior to the infusion and results reported on the electronic case report form (eCRF) when available
  - Note: results from any analyses conducted on tissue from other biopsies or unplanned surgical resections for the duration of a patient's follow-up should be recorded in eCRF and remaining tissue may be requested for analysis

- The biopsy needle and catheter will be placed by the trained operating surgeon with stereotactic guidance using a MRI-compatible stereotactic head frame or a similar frameless device, and an Food and Drug Administration (FDA) cleared stereotactic guidance system guided by a pre-operative MRI.

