### **7.1.2 Non-Treatment Emergent Adverse Events**

Any AE occurring after a patient provides informed consent that is related to the non-SOC screening procedures (eg, PV vaccination booster) and biopsy procedure will be assessed, recorded in the patient's source documents and the eCRF with attribution, regardless of causality or seriousness (non-TEAEs).

Any AE occurring from the time of informed consent to start of PVSRIPO infusion that are not considered related to a study required non-SOC screening procedure, should be reported as medical history. For example, if a patient had new onset seasonal allergies requiring medication after signing of ICF but before Screening Period 2, it would be reported as medical history.

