#### **8.4.5 Safety Analysis**

The full safety analysis set will include all patients who were administered at least one dose of the PVSRIPO. The safety of study-required pre-infusion procedures including catheter placement, will also be summarized.

Separate summaries will be prepared for the primary safety analysis set, which is patients who received PVSRIPO and  $\geq 1$  dose of pembrolizumab. Patients who received PVSRIPO alone will be summarized separately (secondary safety analysis).

Summaries of TEAE will begin at the time of PVSRIPO infusion. Adverse events considered related to screening or other pre-infusion procedures that are not SOC (eg, PV booster, biopsy prior to infusion, catheter placement without PVSRIPO infusion) will be summarized separately (screening data set).

All safety endpoints for patients receiving PVSRIPO and  $\geq 1$  dose of pembrolizumab may be summarized overall and by the number of pembrolizumab treatments received while on study (eg, 1, 2 to 3, 4 to 6, etc.).

Adverse events will be summarized by highest grade per patient and by attribution according to CTCAE v5.0, using the latest version of MedDRA preferred term as event category and MedDRA primary system organ class body term as Body System category. Unless otherwise stated, adverse events will be displayed in terms of frequency tables by treatment group by decreasing frequency. Each patient will be counted only once within each preferred term or system organ class. If a patient experiences more than one AE (or laboratory value) within a preferred term or system organ class for the same recording period, only the AE with the strongest relationship or the worst severity, as appropriate, will be included in the summaries of relationship and severity.

Events meeting the criteria for a DLT or SAE, leading to discontinuation, resulting in death, etc., will be reported in additional summaries. Changes from baseline over time and abnormal laboratory values, vital signs and NANO and KPS will also be reported.

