**4.2.        SAFETY ANALYSIS SET**

The SAF includes all enrolled participants who had an infusion catheter placed. This will be the primary population used for the safety analyses. Participants in the SAF set will be analyzed based on the treatment received.

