### 5.8.1. Adverse Events

AEs will be mapped to a Medical Dictionary for Regulatory Activities (MedDRA) version 23.1 by system organ class and PT. If a participant experiences multiple events that map to a single PT, the greatest severity and strongest assessment of relation to a study drug will be assigned to the PT for the appropriate summaries. AE severity will be assessed according to the CTCAE version 5. If CTCAE grading does not exist for an AE, the severity of the AE will be graded as mild (1), moderate (2), severe (3), life-threatening (4), or fatal (5).

The number of participants for the following groups will be summarized by overall:

- Any TEAE
- Any TEAE related to a study drug or catheter with sub bullets for TEAEs related to catheter placement, lerapolturev or pembrolizumab
- Any TESAE
- Any TESAE related to a study drug or catheter with sub bullets for TESAEs related to catheter placement, lerapolturev or pembrolizumab
- Any DLTs
- Any AESIs for lerapolturev
- Any irAEs for pembrolizumab
- Any TEAEs leading to discontinuation of study treatment
- Any TEAE with grade  $\geq 3$
- Any TEAE with grade  $\geq 3$  related to study drug or catheter with sub bullets for TEAEs with grade  $\geq 3$  related to catheter placement, lerapolturev or pembrolizumab
- Any Grade 5 TEAEs
- Any Grade 5 TEAEs related to study drug or catheter with sub bullets for Grade 5 TEAEs related to catheter placement, lerapolturev or pembrolizumab

The occurrence of TEAEs and TEAEs related to study drug or catheter will be summarized by PT, system organ class, and severity. All AEs reported will be listed for individual participants showing both verbatim and PT. All AEs that occurred prior to catheter placement will be excluded from the tables but will be included in the listings.

Missing onset dates will be imputed as previously outlined in Section 3.2.3.2 as required to determine TEAEs.

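### The SAP drops, without declaring it, the protocol's separate summary of adverse events from the polio booster, the biopsy and catheter placement without infusion

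*SAP*

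**What the plan says.** **Protocol.** Section 7.1.2 requires recording, with attribution, of "Any AE occurring after a patient provides informed consent that is related to the non-SOC screening procedures (eg, PV vaccination booster) and biopsy procedure". Pre-infusion events that are not related to a required non-standard-of-care procedure go to medical history instead. Section 8.4.5 says that events "related to screening or other pre-infusion procedures that are not SOC (eg, PV booster, biopsy prior to infusion", and also those of a catheter placed without infusion, "will be summarized separately (screening data set". It adds: "The safety of study-required pre-infusion procedures including catheter placement, will also be summarized". The synopsis (Statistical Methods) and the opening of Section 8 repeat the promise to keep these events apart from treatment-emergent adverse events (TEAEs). Section 7.1.3 repeats it for catheter-only events.

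**SAP.** Section 5.8.1 says: "All AEs that occurred prior to catheter placement will be excluded from the tables but will be included in the listings". Section 3.2.6 defines a TEAE by onset at or after placement of the catheter, whatever the cause. Section 4.2 says: "The SAF includes all enrolled participants who had an infusion catheter placed". Section 5 has all summary tables present the overall population. Section 6 lists changes and dropped analyses, and the pre-infusion summary is not among them. Section 8 of the protocol gives the SAP precedence where the two differ.

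**The concern.** The study asks for a polio booster before infusion, and for an invasive brain biopsy in anyone without histology from the preceding 6 weeks. On the biopsy day, "a biopsy will be conducted prior to catheter placement and PVSRIPO infusion". The harms of these steps belong to the safety of the regimen, and the protocol planned to count them on their own.

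The usual reason for leaving pre-treatment events out of tables is that they are background noise. That reason is weak here. Because unrelated pre-infusion events are diverted to medical history, the pre-catheter AEs on file should be mainly the procedure-related ones that the protocol wanted summarized.

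At stake is whether the report gives a planned numerator, denominator and rate for booster and biopsy harms, and whether the TEAE tables mix procedure events and catheter-only participants with the experience of infused participants.

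**Working it through.** No arithmetic beyond counting applies. The check sets the protocol's commitment against the SAP's definitions and table list.

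**Step 1: count the planned outputs (SAP Section 10).**
- AE tables: 14.3.1.1 to 14.3.1.11, so 11. All are treatment-emergent and on the Safety Set.
- Tables of pre-catheter AEs, or of AEs by booster or biopsy: 0.
- Tables on the screening set: 1 (14.1.1.1), which is disposition.
- AE listings: 1 (16.2.7.1).
- Analyses declared as dropped in SAP Section 6, item 3: 8 (a to h). The pre-infusion summary is not one of them.

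**Step 2: check the attribution lines.** The overall AE summary in SAP 5.8.1 has relatedness lines for catheter placement, lerapolturev and pembrolizumab. It has none for booster or biopsy.

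**Step 3: follow each kind of event.** The protocol sends the booster, biopsy and catheter-only events below to the separate summary.

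| Event | Where the SAP puts it |
|---|---|
| Booster reaction before the catheter; catheter placed later | Listing only |
| Booster reaction in someone who never has a catheter | Listing only; the person is outside the Safety Set, so no AE table can include the event |
| Booster reaction with onset date wholly missing, or only the day missing in the month of dosing | Moved to the dose date (Section 3.2.3.2) and so a TEAE, unless a recorded end date before dosing pulls it back |
| Biopsy event timed before placement, with biopsy, placement and infusion on one day | Listing only |
| The same biopsy event with no onset time | Assumed to follow placement (Section 3.2.6, TEAE definition) and so a TEAE |
| Biopsy event with onset after placement | TEAE, with no biopsy line |
| Event in a participant with a catheter but no infusion | Meets the catheter condition of the Safety Set and is pooled with infused participants |

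**Step 4: limits of the untimed-onset rule.** The rule covers events that start on SAP Day 1, the day study drug is started. Protocol 5.2.2 allows infusion on the day after placement, or up to 72 h after placement with approval. An untimed event on a later infusion day really does follow placement. The inconsistency between the fourth and fifth rows therefore arises only when all three procedures share a calendar day.

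**Step 5: catheter-only participants.** SAP 4.2 speaks of enrolled participants, while the protocol calls a patient who is not infused a screen failure. If such a person counts as enrolled, their events are pooled with those of infused participants. If not, their events reach no AE table. Neither reading gives the separate summary that protocol 7.1.3 and 8.4.5 call for.

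**The case against.** The strongest reply is that the SAP governs, the omitted output is descriptive, and nothing is lost. The sentence in Section 5.8.1 keeps these events in the listings, and Section 9 of the SAP prepares listings for all participants. Catheter harms also have their own lines among TEAEs, serious TEAEs, events of grade 3 or higher, and grade 5 events. All of this is correct. The precedence clause settles which text is followed, but it does not make the departure visible. Section 6 exists for that purpose and does not mention it. The catheter lines do not cover the booster or the biopsy, and they do not separate participants who were never infused.

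Some stronger readings are tempting, but the documents do not support them:
- A reader might infer that booster and biopsy harms are tabulated nowhere, or are deleted. Events with onset after placement, or imputed there, do enter the TEAE tables, and the rest stay in listing 16.2.7.1.
- A reader might infer that biopsy events are generally sorted by whether a time was written down. That holds only in the same-day case of Step 4.
- The biopsied patient who never gets a catheter is a marginal example, because the protocol places the catheter directly after the biopsy, before the diagnosis is known. Boosted participants who fail screening before placement are the more important group.
- A reader might assume that every consented patient is boosted. The booster follows consent and the screening blood draws, so some may leave before it.

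**Conclusion.** The point holds in this form. The SAP removes a promised safety summary by a stated rule and does not declare the removal. Its size is 0 of 11 AE tables for pre-infusion procedures, and a safety set that shuts out anyone without a catheter. Booster and biopsy events are split between a listing and the TEAE tables by onset relative to the catheter, and in the same-day case by whether a time was recorded.

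No event rate or interval can be attached to this. The documents give neither the number boosted nor the number biopsied, and SAP Section 6 says that full enrolment was not reached.

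The conclusion rests on the SAP's table list being complete. It should be corrected, but it does not touch the efficacy analyses, and the underlying records remain available.

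**What to change.** Replace the exclusion sentence in SAP 5.8.1, and add one table to Section 10 on the screening analysis set. The table should:
- cover AEs from consent to the start of infusion that are attributed to the booster, the biopsy or catheter placement;
- show them by procedure, preferred term and worst grade;
- use the number who underwent each procedure as the denominator.

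Show participants with a catheter but no infusion separately from the TEAE tables, and state in SAP 4.2 whether they count as enrolled. Because the SAP starts the TEAE window at placement, an event between placement and infusion in an infused participant would appear in both displays, so a footnote should say so.

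If the sponsor decides against the table, the least that is needed is an entry in SAP Section 6 that declares the omission and gives the reason. That would cure the silence but not restore the summary.

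The cost is one descriptive table. Protocol 7.1.2 already has these events recorded with attribution, but the interventions named for attribution in protocol 7.1 do not include the booster or the biopsy. The sponsor should check the eCRF. If it has no such category, the attribution must be taken from the recorded AE entries before database lock.

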### 5.8.2. Clinical Laboratory Assessments

AEs for clinical labs will be characterized according to CTCAE version 5 (when possible) and shift in grade from baseline to the worst post-baseline value will be summarized. Both scheduled and unscheduled assessments will be used to identify the worst post-baseline values.

The following categories of abnormal hepatic laboratory values will be evaluated for any occurrence among all post baseline assessments.

- Alanine Aminotransferase (ALT) and/or Aspartate Aminotransferase (AST)  $> 3 \times$  upper limit normal (ULN), Alkaline Phosphatase (ALP)  $< 2 \times$  ULN, and Total Bilirubin  $\geq 2 \times$  ULN

- AST > 3, 5, 8, 10, and 20 x ULN, and 5 x ULN for more than 5 weeks
- ALT > 3, 5, 8, 10, and 20 x ULN, and 5 x ULN for more than 5 weeks
- Total Bilirubin > 1.5 or  $\geq 2$  x ULN

Listings of all laboratory data with normal reference ranges, and CTCAE grades (when possible) will be provided.

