7. KPS  $\geq 70$  at screening and baseline.
8. Undergone prior vaccination against PV and received a boost immunization with trivalent IPOL® (Sanofi-Pasteur SA) at least 1 week, but less than 6 weeks, prior to administration of PVSRIPO (within 6 months of PVSRIPO retreatment). Note: Patients who are unsure of their prior vaccination status/who have not been vaccinated must provide proof of vaccination and/or evidence of anti-PV immunity prior to enrollment, as applicable.
9. Ability to safely discontinue anti-coagulant therapy(ies) prior to biopsy/catheter placement, as required per site/surgical guidelines, in the opinion of the investigator.
10. Hemoglobin  $\geq 9$  g/dL prior to biopsy/catheter placement.
11. Platelet count  $\geq 100,000/\mu\text{L}$  (unsupported);  $\geq 125,000/\mu\text{L}$  (can be supported via platelet transfusion) at biopsy/catheter placement and/or with a Sponsor-approved bone marrow stimulant/colony stimulating factor, eg, romiplostim).
12. ANC  $\geq 1000/\mu\text{L}$  prior to biopsy/catheter placement.
13. Creatinine  $\leq 1.2 \times \text{ULN}$  prior to biopsy/catheter placement.
14. Total bilirubin, ALT, AST, ALP  $\leq 2.5 \times \text{ULN}$  prior to biopsy/catheter placement.
15. PT and aPTT  $\leq 1.2 \times \text{ULN}$  prior to biopsy/catheter placement.
16. If undetectable ATT IgG at screen, Tdap booster vaccine  $> 1$  week prior to biopsy/catheter placement.
17. Patients must be willing and able to understand and provide written informed consent.

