#### Baseline Value

For purposes of analysis, the baseline value is defined as the last non-missing value obtained prior to calendar day of lerapoltrev infusion.

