#### Safety

- 14.3.1.1 Overall Summary of Treatment-Emergent Adverse Events, Safety Set
- 14.3.1.2 Treatment-Emergent Adverse Events by System Organ Class, Preferred Term, and Greatest Severity, Safety Set
- 14.3.1.3 Treatment-Emergent Adverse Events by Preferred Term in Descending Frequency, Safety Set
- 14.3.1.4 Treatment-Emergent Adverse Events Related to Study Drug or Catheter by System Organ Class, Preferred Term, and Greatest Severity, Safety Set
- 14.3.1.5 Treatment-Emergent Adverse Events Related to Study Drug or Catheter by Preferred Term in Descending Frequency, Safety Set
- 14.3.1.6 Treatment-Emergent Serious Adverse Events by System Organ Class, Preferred Term and Greatest Severity, Safety Set
- 14.3.1.7 Treatment-Emergent Serious Adverse Events Related to Study Drug or Catheter by System Organ Class, Preferred Term, and Greatest Severity, Safety Set
- 14.3.1.8 Treatment-Emergent Dose Limiting Toxicities by System Organ Class, Preferred Term and Greatest Severity, Safety Set
- 14.3.1.9 Treatment-Emergent Adverse Events of Special Interest for Lerapoltrev by System Organ Class, Preferred Term, and Greatest Severity, Safety Set
- 14.3.1.10 Treatment-Emergent irAEs for Pembrolizumab by System Organ Class, Preferred Term, and Greatest Severity, Safety Set
- 14.3.1.11 Treatment-Emergent Adverse Events Leading to Discontinuation of Study Treatment by System Organ Class, Preferred Term, and Greatest Severity, Safety Set
- 14.3.4.1 Summary of Grade Shifts in Laboratory Abnormalities – Hematology, Safety Set
- 14.3.4.2 Summary of Grade Shifts in Laboratory Abnormalities – Chemistry, Pancreatic and Thyroid, Safety Set

- 14.3.4.3 Number of Participants with at Least One ALT, AST, or Total Bilirubin Above Upper Limit of the Normal Range Post-Baseline, Safety Set
- 14.3.4.4 Summary of Vital Signs by Visit, Safety Set
- 14.3.4.5 Summary of Karnofsky Performance Status by Visit, Safety Set
- 14.3.4.6 Summary of Neurologic Assessment in Neuro-Oncology Score by Visit, Safety Set

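### The bilirubin and combined liver rows of SAP Table 14.3.4.3 are not split by baseline, although patients may enter with bilirubin and ALP up to 2.5 × ULN

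*SAP*

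**What the plan says.** Protocol 4.1, inclusion criterion 14, sets one ceiling for "Total bilirubin, ALT, AST, ALP": 2.5 × ULN before biopsy or catheter placement.

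SAP 5.8.2 then defines categories of abnormal liver values that "will be evaluated for any occurrence among all post baseline assessments":

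- ALT and/or AST above 3 × ULN, with ALP below 2 × ULN and total bilirubin at or above 2 × ULN (the combined pattern);
- "AST > 3, 5, 8, 10, and 20 x ULN, and 5 x ULN for more than 5 weeks", and the same for ALT;
- "Total Bilirubin > 1.5 or" at or above 2 × ULN.

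None of these carries a baseline condition, an alternative expressed as a multiple of baseline, or a rule for patients who enter with an abnormal value. The SAP does not say whether the three parts of the combined pattern must come from the same sample. The planned output, Table 14.3.4.3, is titled "Number of Participants with at Least One ALT, AST, or Total Bilirubin Above Upper Limit of the Normal Range Post-Baseline", again with no baseline condition.

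Baseline is available for this purpose. SAP 3.2.6 states that "the baseline value is defined as the last non-missing value obtained prior to calendar day of lerapoltrev infusion". SAP 5.8.2 itself uses baseline for CTCAE grade shifts to the worst post-baseline value (chemistry in Table 14.3.4.2) and promises listings of all laboratory data.

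**The concern.** The cut-offs for bilirubin, and the ALP condition in the combined pattern, lie below the level at which a patient may enter. A count in those rows can therefore reflect the state at entry rather than a change after treatment, and the combined row can leave out a patient because of an ALP that was already raised.

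Protocol 7.5.3 names immune-mediated hepatitis among the pembrolizumab reactions and asks for monitoring of hepatic function, so this table will be read for a liver signal. The combined pattern is the only planned summary that joins aminotransferases, ALP and bilirubin in the same patient. In a small single-arm trial with no control group to show the background rate, one patient in that row draws attention. The reader should be able to see from the table whether the abnormality was new.

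**Working it through.** The documents give no figure for these liver categories, so there is nothing to reproduce. The check sets the entry ceiling against each cut-off.

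**Inputs.** Entry ceiling 2.5 × ULN for all four tests (Protocol 4.1, criterion 14). Cut-offs and counting rule from SAP 5.8.2. It is assumed that the baseline value respects the entry ceiling.

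**Step 1: which eligible values meet a condition with no change at all** (multiples of ULN)

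| Row or condition | Cut-off | Eligible values affected |
|---|---|---|
| Bilirubin, first row | > 1.5 | > 1.5 to 2.5 are counted |
| Bilirubin, second row | ≥ 2 | 2.0 to 2.5 are counted |
| ALT or AST rows | > 3 and higher | none, since 2.5 < 3 |
| ALP part of combined pattern | < 2 | 2.0 to 2.5 fail it |

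**Step 2: example profiles run through the combined pattern**

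| Profile | ALT | ALP | Bilirubin | Combined row | Other rows |
|---|---|---|---|---|---|
| Unchanged eligible | 2.5 | 1.9 | 2.5 | no (ALT not > 3) | both bilirubin rows |
| ALT 2.4 to 3.1, bilirubin flat | 3.1 | 1 | 2.2 | yes | ALT > 3, both bilirubin rows |
| Large rise, ALP flat at entry value | 12 | 2.3 | 6 | no (ALP not < 2) | ALT > 3, 5, 8, 10; both bilirubin rows |
| Large rise, ALP normal | 12 | 1 | 6 | yes | ALT > 3, 5, 8, 10; both bilirubin rows |

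Carry-over without any change is thus confined to the two bilirubin rows. The combined row always needs a new aminotransferase rise, but its bilirubin part can be pre-existing (second profile). The third and fourth profiles differ only in ALP, and only the fourth reaches the combined row. If the parts need not be concurrent, a later ALP below 2 × ULN would bring the third profile in as well.

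**Step 3: how many patients.** The documents give no share q of patients entering with bilirubin above 1.5 × ULN, so q is an assumption. With n = 30 as an illustration, and each such patient's bilirubin staying above the cut-off:

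expected carried-over counts = 30q; P(at least one) = 1 − (1 − q)^30.

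| Assumed q | Expected | P(at least one) |
|---|---|---|
| 0% | 0 | 0 |
| 1% | 0.3 | 1 − 0.99^30 = 0.26 |
| 3% | 0.9 | 1 − 0.97^30 = 0.60 |
| 5% | 1.5 | 1 − 0.95^30 = 0.79 |
| 10% | 3.0 | 1 − 0.90^30 = 0.96 |

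At n = 30 one patient is 1/30 = 3.3 percentage points. The true denominator is not known. The safety set is everyone with a catheter placed (SAP 4.2), replaced patients come on top of the 30 (Protocol Synopsis), and SAP section 6 records that full enrolment was not reached.

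**The case against.** The strongest reply is that the SAP does not ignore baseline. The section that defines these categories also plans grade shifts from baseline and full listings, and in a trial of this size a reader can look up whether a raised bilirubin was there at entry. An any-occurrence screen on absolute thresholds is also inclusive by design. Much of this stands: the shifts and listings do offset the problem in part. They do not settle it, because the shift table works one test at a time and cannot show whether the bilirubin part of a combined-pattern case was pre-existing, and a listing leaves the reader to rebuild the published count.

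A reader might also infer two stronger things.

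- *That the SAP would report baseline disease as treatment-emergent liver injury.* It does not. It calls these categories abnormal laboratory values, and the table title says only that they are post-baseline. TEAEs, irAEs and DLTs have their own tables. Protocol 7.1.1 makes newness or worsening from baseline one of the considerations in judging clinical significance for AE reporting.
- *That real liver injury would be missed.* The third profile above is absent from one row but present in four ALT rows and both bilirubin rows. It could also be reported as an AE or irAE or, within the assessment window, as a DLT through the drug-induced liver injury item.

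A last fair objection concerns the remedy. Restricting counts to patients below the cut-off at baseline would hide real deterioration: a bilirubin going from 2.1 to 10 × ULN would leave both bilirubin rows. That objection is right, and the change proposed here avoids it.

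**Conclusion.** The point holds as a minor matter of presentation. Three statements follow directly from the text:

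1. A stable eligible bilirubin above 1.5 × ULN is counted in one or both stand-alone bilirubin rows.
2. A pre-existing bilirubin of 2.0 to 2.5 × ULN can complete the combined pattern once ALT or AST newly exceeds 3 × ULN.
3. An entry ALP of 2.0 to 2.5 × ULN keeps a patient out of the combined row for as long as it stays at or above 2 × ULN.

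The ALT and AST rows are unaffected. The number of patients concerned cannot be derived from the documents and may be zero; the probabilities above rest wholly on the assumed q and on n = 30. It would also go too far to say that one such case changes the trial's hepatic conclusion. The SAP is descriptive and has no decision rule for liver findings. Efficacy and sample size are untouched.

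**What to change.** In SAP 5.8.2 and Table 14.3.4.3:

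1. Keep the planned any-occurrence counts, and remove no patient because of a raised baseline.
2. Split each bilirubin count by whether the baseline value already met that cut-off, and split the combined-pattern count by whether baseline bilirubin was already at or above 2 × ULN.
3. For patients whose baseline already met the cut-off, show the post-baseline maximum as a multiple of baseline, so that worsening stays visible.
4. Add a row for ALT and/or AST above 3 × ULN with bilirubin at or above 2 × ULN regardless of ALP, using the same timing convention as the combined row.
5. For every patient in that added row, list baseline and peak ALT, AST, ALP and bilirubin.

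The cost is a few extra columns, one extra row and a short listing, all from data already collected. No clinical rule changes. If no patient entered above a cut-off, the planned counts stay exactly as they are.
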